7.2. Exclusion criteria

Participants who self-report meeting ANY of the following criteria at time of recruitment will be excluded from study participation:

1. Concurrent psychotherapy
2. Current self-reported diagnosis of any of the following conditions, including receiving or waiting for treatment:
 - Alcohol abuse/dependence
 - Substance abuse/dependence
3. Self-reported diagnosis of current or history of bipolar disorder or psychosis at any time
4. Taking antidepressants or anxiolytic medications at a stable dose for less than six weeks
5. Severe post-traumatic stress disorder (PTSD, assessed as a score of 17 or higher in total for the first six questions AND a score of 2 or higher on the seventh question of the adapted International Trauma Questionnaire⁵⁸; ITQ)
6. Suicidal thoughts and self-harm assessed by a combination of PHQ-9³⁸ **question 9** score of 1 or higher and a yes to question R1a and/or R1B, and a yes to either question R2 and/or R3 (detailed below):
 - *R1a = In the last 2 weeks have you been experiencing regular thoughts about suicide?*
 - *R1b = In the last 2 weeks have you been experiencing regular thoughts about self-harm?*
 - *R2 = In the last 2 weeks have you had any intention to hurt or kill yourself?*
 - *R3 = In the last 2 weeks have you made any plans to harm yourself or end your life?*

People who are excluded from the study will be provided with information signposting them to relevant advice or support. If a person indicates that they have intention to, or made plans to, hurt or kill themselves in the past 2 weeks the screening form will enable the person to volunteer their contact details and GP details if they would like to receive a phone call from a member of the research team, and potentially be referred to their GP.

The PWPs will follow a separate risk management protocol to assess and support any individuals who are identified as being at risk during the study.

USA-specific detail

For participants recruited in the USA, automated signposting to support services will be tailored to services specific to the local study population in the USA.

During screening, if individuals endorse the exclusion criteria of active suicidality, severe PTSD or diagnosis of bipolar disorder, substance abuse or psychosis they will be provided with contact information for the college health center counseling services, as well as community emergency resources.

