GAD-7 ³⁷		X																		X	X	
Medical history & concomitant medications		X																		X	X	
WEMWBS Short Form ³⁹		X																		X	X	
WSAS ⁴²		X																		X	X	
Adapted LIDAS ⁴³		X																		X	X	
Adapted GAD ⁴⁴		X																		X	X	
Intervention use and experience																				X		
Treatment and hospitalisations																				X	X	
Mechanism Measures:																						
Self-Compassion Scale ⁴⁸ (self-kindness, common humanity, self-judgement subscales)		X																		X	X	

The Calming Minds Trial

IRAS ID: 356635

ISRCTN No: 10569526

TIMEPOINT (t) unit = Days	Pre- baseline	Baseline	Allocation	Post-allocation																Follow- up 1	Follow- up 2	
				Intervention period																		
				t+ 7 ^a	t+ 14 ^a	t+ 21 ^a	t+ 28 ^a	t+ 35 ^a	t+ 42 ^a	t+ 49 ^a	t+ 56 ^a	t+ 63 ^a	t+ 70 ^a	t+ 77 ^a	t+ 84 ^a	t+ 91 ^a	t+ 98 ^a	t+ 105 ^a				
5 Facet Mindfulness Questionnaire ⁵¹ (short form, 2 subscales)		X																		X	X	
Self-Reported Habit Index ⁴⁷ for RNT		X																		X	X	
Attitudes towards self scale ^{45,46} (overgeneralisation and self criticism subscales)		X																		X	X	
Self efficacy/mastery & problem clarification ^{49,50}		X																		X	X	
Flow Proneness Questionnaire ⁵² – leisure subscale only		X																		X		
Linguistic Analysis		X																		X		
EMA assessment of RNT (via mPath)		X																		X		
Moderators:																						
Childhood loss		X																				
Early adversity (including Childhood Trauma Screener ⁵⁹ ; CTS)		X																				
Adult trauma and stress		X																				

The Calming Minds Trial

IRAS ID: 356635

ISRCTN No: 10569526

	Pre-baseline	Baseline	Allocation	Post-allocation														Follow-up 1	Follow-up 2	
				Intervention period																
TIMEPOINT (t) unit = Days	Undefined	t-28 ^a	t0	t+ 7 ^a	t+ 14 ^a	t+ 21 ^a	t+ 28 ^a	t+ 35 ^a	t+ 42 ^a	t+ 49 ^a	t+ 56 ^a	t+ 63 ^a	t+ 70 ^a	t+ 77 ^a	t+ 84 ^a	t+ 91 ^a	t+ 98 ^a	t+ 105 ^a	t+112 days ^b	t+365 days ^c
(including adapted adverse events questionnaire ⁴⁶)																				
Sleep ⁶⁰		X																		
UCLA Loneliness Short ⁶¹		X																		
Big Five Inventory-10 ⁶²		X																		
Cognitive Failures Questionnaire 2.0 ⁶³		X																		
Avoidance and Activation ⁶⁴		X																		
Need for closure scale (avoidance and predictability subscales) ^{65,66}		X																		
Discrimination scale ⁶⁷		X																		

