INTERVENTION/TREATMENT PERIOD																				
Allocation				X																
Intervention (via MyDataHelps)					→															
During intervention micro-assessments:																				
PHQ-2				X	X	X	X	X		X		X		X		X		X		
GAD-2				X	X	X	X	X		X		X		X		X		X		

The Calming Minds Trial

IRAS ID: 356635

ISRCTN No: 10569526

	Pre-baseline	Baseline	Allocation	Post-allocation																Follow-up 1	Follow-up 2
				Intervention period																	
TIMEPOINT (t) unit = Days	Undefined	t-28 ^g	t0	t+ 7 ^a	t+ 14 ^a	t+ 21 ^a	t+ 28 ^a	t+ 35 ^a	t+ 42 ^a	t+ 49 ^a	t+ 56 ^a	t+ 63 ^a	t+ 70 ^a	t+ 77 ^a	t+ 84 ^a	t+ 91 ^a	t+ 98 ^a	t+ 105 ^a	t+112 days ^b	t+365 days ^c	
Condensed (2-3 item version) of self report and brief problem description measures of mechanisms and brief outcome measures of RNT				X	X	X	X	X		X		X		X		X		X			
mPath engagement prompts									X		X		X		X		X				
OTHER ACTIVITIES																					
Researcher / PWP (UK) / Coach (USA) contact points		X ^d		X ^e		X ^e						X ^e									
Withdrawals, including free text reasons																					
Participant contact log																					
Qualitative interview																			X ^h	X ^h	
Adverse events																					
Suicide Risk assessment																					

a = Schedule begins when participant reinstalls mPath with code provided at point of randomisation, +4 day window for completion, b = Schedule begins from randomisation for all assessments other than EMA which begins when participant reinstalls mPath with code provided at point of randomisation, +4 week window for completion, c = Schedule begins from randomisation, +6 week window for completion, d = Researcher contact to help participant set up and use mPath App, e = Minimum of 3 sessions planned for approximately at the start of the intervention, 1/3 through and 2/3 through the intervention. Additional sessions may also be scheduled based on participant need. Ad-hoc interactions between PWP/coaches and participants will also occur in response to identification of potential risk/safety events, f = Participant will complete PHQ-9 and if scoring 1 or more on question 9, additional suicide risk questions will be presented, g = Maximum 28 days to complete baseline questionnaires (this period may be extended in extenuating circumstances if requested by a participant). Minimum time to complete baseline is 10 days to allow sufficient time to complete the EMA, h = subset of UK participants only.

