3. **MANDATORY:** In parallel, participants will receive information required to install the m-Path App on their smart phone which is required for the ecological momentary assessment (EMA) measures^{1,2}. These are another way of assessing their RNT in the real-world, as a means to measure its frequency and occurrence in daily life and as a way of providing information to their PWP (UK)/coach (USA), who will have a ‘view only’ user account on mPath to see data entered by participants. Participants do not need to provide any personal identifiable data to set up m-Path but will be provided with a unique invitation code. Once installed, participants will be asked to complete EMA (via m-Path) for 10 consecutive days. Participants will receive 6 prompts each day from the app to complete brief questions asking about RNT, mood, stress and habit, at pseudo random intervals throughout the day. There is a dashboard so participants can view the data they are entering in the EMA. Participants will need to complete a minimum of 60% of total EMA prompts (i.e., 36 prompts) to be able to proceed to randomisation. Any participant who has completed <20% of prompts (i.e., 12 or fewer) after 10 days is unlikely to be engaged in the study and will not proceed to randomisation. Any participant who has completed ≤20% and <60% of prompts by day 10, could raise this completion level sufficiently with more time and will therefore be given 4 additional days to complete a minimum of 36 EMA prompts on the m-Path app. If they complete a minimum of 36 prompts by the end of the additional 4 days, they will be able to proceed to randomisation. Participants will be sent emails to notify them of their status as required (e.g. reminder to start if not yet started, being allowed more time, not enough completed to proceed).

Progress on completing the EMA will be monitored by the research team at LMU. LMU will provide regular reports to the ExeCTU and UCLA study team of their participants (identified by unique invitation code (as a proxy for participant ID (PID) number)) including: a list of participants signed up to the app, the date the first prompt was sent to each participant and summary data to indicate completion rates at various stages of the EMA process. The reports will be used to send reminders/status updates to participants about their progress with the prompts, and to update

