12.1. Definitions

Because the current intervention is digital self-help with PWP(UK)/ coach(USA) support, rather than a medicinal product and involves no biological agent, it is not appropriate to report all adverse events (defined as any untoward medical occurrence). Rather, as a psychological intervention, appropriate adverse events would include those related to mental state and behaviour. We will therefore not report

non-serious adverse events but will report serious adverse events (SAEs) within all intervention groups under our own study-specific definition (see **Table 1**).

As this is a low risk study with no known adverse events associated with the intervention, all related adverse events are unexpected of the intervention.

Table 1: Definitions of adverse events

Term	Definition
AE	Any unintentional, unfavourable clinical sign or symptom, or any new illness or disease or the deterioration of existing disease or illness (not recorded/reported in this study).
SAE	For the purposes of this study, a Serious Adverse Event (SAE) is defined as any of the following events: 
 • Death (including suicide). • Suicide attempt. • New self-harm or an increase in frequency, intensity or duration of self-harm (self-harm is defined as anything with the intention to harm self without the intention to end life including but not limited to; cutting, burning, scratching, hitting). • Serious accident or violent incident requiring emergency medical assistance (including presentation at Accident and Emergency, hospital treatment or ambulance/paramedic callout). • Referral to crisis care or admission to psychiatric hospital. • Admission to A&E for overdose or excessive alcohol or drug use.
Related Unexpected SAE (RUSAЕ)	Any event which meets one or more of the above SAE criteria AND is assessed as being likely to have been caused by the intervention.

All SAEs will be reported to ExeCTU on a SAE form within REDCap. This must be completed within 24 hours of the investigator becoming aware of the event. All SAEs will be onward reported to the Sponsor by ExeCTU. SAEs which are categorised as unrelated to the intervention will be reported monthly by provision of a trial management group (TMG) report.

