12.3. Reporting Serious Adverse Events

SAEs will be reported from randomisation up until 20 weeks post randomisation (i.e. 16-week follow-up plus the 4-week window allowed for completion of questionnaires).

In a bid to commit to data minimisation (especially of sensitive category data), we will not respond to or report SAEs for non-randomised participants. Depending on the attrition rate during completion of baseline assessments, the number of individuals who do not convert to randomisation could be significant, and therefore beyond the capacity of the research team to follow-up events. Only randomised participants (i.e. those offered the intervention) will be monitored for safety.

In the event a member of the research team becomes aware of a (potential) SAE, a PWP will endeavour to contact the participant by telephone and/or email to enquire about the safety and well-being of the participant, determine whether a SAE has occurred and offer support as described in Section 12. If a SAE has not occurred, the PWP/coach will document it on the risk log, but no further data will be collected.

In the event of a SAE the PWP or site lead will complete a SAE report form on REDCap Academic to capture key information about the event. This will include:

- Event name (brief term describing the event)
- Reason for being an SAE
- Date of occurrence (estimated if exact date unknown)
- Date research team became aware of event
- Detailed description of the event and any actions taken
- Status of the event (ongoing, resolved, death)
- Intensity (mild, moderate, severe)
- Causality (relationship to the study intervention)
- Name and signature of person assigning causality

If a SAE is categorised as related to the intervention, a statement will appear on the SAE form informing the research team that the event is a Related Unexpected SAE (RUSAE) and must be reported to the Sponsor, DMEC and REC following the expedited timeframe (15 days for the DMEC and REC).

If the SAE is ongoing at the time of the initial report, follow-up report forms will be completed until the event is resolved, the participant has died, or the Sponsor and CI agree that no further follow-up is required. Where possible, efforts will be made to ensure any ongoing SAEs are resolved prior to database lock.

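### A serious adverse event caused by a study procedure has no related category and misses the 15-day route; the self-harm criterion also lacks a stated comparison period

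*Protocol*

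**What the plan says.** **Relatedness.** The definitions table in section 12.1 makes an event a related unexpected SAE if it meets an SAE criterion "AND is assessed as being likely to have been caused by the intervention". The SAE form described in section 12.3 has one causality item, "Causality (relationship to the study intervention". Section 12.1 also treats every related event as unexpected, so the relatedness judgement alone decides the reporting route.

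**Routes.** All SAEs go to the clinical trials unit within 24 hours and then to the sponsor (12.1). Those judged unrelated to the intervention are reported monthly through the TMG report (12.1). Those judged related go to the DMEC and the REC within 15 days (12.1, 12.3). The DMEC and TSC also see aggregate SAE data twice a year (12.3).

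**Window.** SAEs are reported only for randomised participants, from randomisation to 20 weeks (12.3).

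**Self-harm.** One SAE criterion is "New self-harm or an increase in frequency, intensity or duration of self-harm". The only screening question specific to self-harm thoughts is R1b, "In the last 2 weeks have you been experiencing regular thoughts about self-harm" (7.2). Under the footnotes to Table 3 it is reached only "if scoring 1 or more on question 9, additional suicide risk questions will be presented" in relation to the PHQ-9. Exclusion needs a positive PHQ-9 item 9, "a yes to question R1a and/or R1B, and a yes to either question R2 and/or R3". An event that a Psychological Wellbeing Practitioner (PWP) or coach judges not to be an SAE is noted on the risk log and no further data are collected (12.3). Sections 12 and 14.1 place that log outside the research data.

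**The concern.** Participants are exposed to more than the online therapy. They answer repeated questions on negative thinking, mood and problems, partly through a phone app that prompts them several times a day. If one of these procedures contributes to an SAE, the form gives the assessor nowhere to say so. The honest answer to the single causality item is that the intervention did not cause the event, and that answer switches off expedited review by the DMEC and REC. A pattern of procedure-related events would then be hard to see, because aggregate reports would mix them with events that have nothing to do with the trial.

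The self-harm criterion raises a lesser issue of the same kind. It asks whether behaviour has changed but does not say compared with when. The SAE count for this criterion then depends on what a participant recalls after the event, and in the UK on the reading of a PWP who knows the allocation (5.1.2, 8.4). A judgement that an act was not new and not increased leaves no entry that the DMEC could review.

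**Working it through.** No figure in the plan underlies this point, so the check sets sections side by side, with a little arithmetic on exposure.

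**1. Which procedures fall inside the SAE window (randomisation to 20 weeks)?**
- Micro-assessments at weeks 1, 2, 3, 4, 5, 7, 9, 11, 13 and 15: 10 occasions (8.5.1). Inside.
- Engagement prompts at weeks 6, 8, 10, 12 and 14: 5 occasions (8.5.1). Inside.
- Week-16 questionnaires, including the writing tasks (3.3.3, Table 3), with a 4-week completion window: 16 + 4 = 20 weeks (8.5.2). Inside.
- Week-16 EMA for 10 to 14 days (8.5.2). Section 8.3 gives the baseline intensity: "Participants will receive 6 prompts each day from the app to complete brief questions asking about RNT, mood, stress and habit". If the same rate applies at week 16, that is 6 × 10 = 60 prompts. It is 6 × 14 = 84 if six a day continue through the four extra days, which the protocol does not state. The EMA schedule runs from reinstallation of the app. With 20 − 16 = 4 weeks (28 days) available, a 14-day EMA starting at week 16 from reinstallation finishes inside the window if reinstallation is delayed by no more than about 28 − 14 = 14 days.
- Baseline questionnaires and baseline EMA come before randomisation. Outside.
- Week-52 questionnaires: 52 > 20. Outside.

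**2. How is an SAE caused only by one of the inside procedures classified?** The definition in 12.1 requires causation by the intervention. Section 4.1 describes the intervention as the online CBT with PWP or coach support, and Table 3 lists assessments separately from it. The event is not related under the definition, and the form offers no other category.

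**3. What route does it take?**

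| Recipient | Judged related | Caused by a procedure, as written |
|---|---|---|
| Trials unit | Within 24 hours | Within 24 hours |
| Sponsor | As soon as practicable | Monthly, through the TMG report |
| DMEC | Within 15 days | Twice-yearly aggregate |
| REC | Within 15 days | No expedited report |

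If the two DMEC reports are evenly spaced, the wait can reach 52 / 2 = 26 weeks, or 26 × 7 = 182 days, against 15 days.

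**4. What supports a judgement that self-harm is new or increased?** Section 12.1 gives no reference period. Table 3 names no measure of self-harm acts. R1b concerns thoughts, covers two weeks, and is conditional on PHQ-9 item 9. The exclusion rule also needs reported intention or plans within the last two weeks, so someone whose self-harm is older than that, or who scores zero on item 9, can be enrolled. Table 3 does list "Medical history & concomitant medications" and a diagnostic assessment at baseline, but the protocol does not say that either covers self-harm acts. The judgement is made by contacting the participant after the event (12.1, 12.3) or, in the USA, from details that the participant self-reports (12.4).

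**The case against.** The protocol calls the trial low risk and says that no health risk is known from the assessments (section 12). All SAEs are still counted whatever their label, the chief investigator reviews aggregate data monthly, and the DMEC may ask for more (13.4). The definition is openly study-specific. These points limit the consequence to the route and the label; they do not supply the missing category. The statement about no known risk covers the CBT modules in the same sentence, and those modules still have a causality field and an expedited route.

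A reader might infer more than the document supports:
- *That self-harm cannot be classified.* It can. The PWP contacts the participant, obtains detail and completes a form, and causality assessors receive training and a work instruction (12.1 to 12.3).
- *That no baseline record of self-harm exists.* The protocol does not show this. Section 13.3.1 says that the measures are set out in separate assessment documents, which are not at hand. Table 3 also has a suicide risk assessment row whose timing cannot be read in the text available. What holds is that Table 3 names no measure of self-harm acts.
- *That all harm from assessments is filed as unrelated.* This applies only from randomisation to 20 weeks. Events during baseline EMA or around week 52 are not reported as SAEs at all, which is a different matter.
- *That section 12 expects harm from the assessments.* It says that people who do not get on well with them will most likely disengage.

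**Conclusion.** The relatedness gap holds. Followed as written, sections 12.1 to 12.3 class a procedure-caused SAE between randomisation and 20 weeks as unrelated and keep it off the 15-day route to the DMEC and REC. Every randomised participant (2192 planned) is scheduled for the procedures concerned. The number of events affected cannot be estimated because the document gives no SAE rate, and it may be very small if the protocol's low-risk view is right. Sample size, power and type I error are untouched.

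The self-harm point is secondary. The criterion is a change without a stated comparison period, and negative judgements are kept out of the trial data. This makes the count for that criterion dependent on recall and hard to audit. The document does not show that events are in fact misclassified. The conclusion assumes that assessors apply the written definitions and that the separate assessment documents and safety work instruction do not already close these gaps.

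**What to change.** 1. In the related-SAE definition (12.1), the causality field (12.3) and the matching reporting text in 12.1 to 12.3, replace causation by the intervention with causation by the intervention or any study procedure. Add a field on the SAE form stating which.
2. In 12.1, state the period against which new or increased self-harm is judged.
3. Record in the trial database each self-harm event that was considered and judged not new or increased, with the reason, and include the count in DMEC reports. A single extra baseline question would not replace this, because it would not capture frequency, intensity and duration.

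**Cost.** A protocol amendment through the applicable UK process (17.10) and UCLA IRB approval, and a small change to the SAE form in both REDCap instances and to the US self-report questions that feed it. There may be a few more expedited reports, and staff must enter some events that now go only to the risk log. No change to the assessments, the sample size or the analysis is needed.

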12.2. Assessing causality of serious adverse events

Causality of SAEs will be assessed by a trained PWP or the chief investigator/site lead in the UK, and the site lead (or clinically qualified delegate) in the USA. Members of the research team who assess causality will be required to complete safety training and will be provided with a study-specific safety work instruction to follow.

SAEs will be assessed for causality within 2 working days of the research team being notified of the event.

